6.1 Study Intervention(s) Administered

The study interventions to be used in this study are outlined in [Table 1](#).

Table 1 Study Interventions

Arm Name	Arm Type	Inter-vention Name	Type	Dose Form	Unit Dose Strength(s)	Dosage Level(s)	Route of Adminis-tration	Regimen	Use	IMP/ NIMP	Sourcing
Active	Experimental	MK-8189	Drug	Tablet	4 mg	All dosage levels	Oral	Panels A, B and C: Titration period, days 1-18 Panel D: Titration period, days 1-15	Experimental	IMP	Provided centrally
Placebo	Placebo Comparator	MK-8189	Drug	Tablet	0 mg	All dosage levels	Oral	Panels A, B and C: Titration period, days 1-18 Panel D: Titration period, days 1-15	Experimental	IMP	Provided centrally

All supplies indicated in [Table 1](#) will be provided per the "Sourcing" row depending upon local country operational requirements. Every attempt should be made to source these supplies from a single lot/batch number. The study site is responsible for recording the lot number, manufacturer, and expiry date for any locally purchased product per local guidelines unless otherwise instructed by the Sponsor.

Refer to Section 8.1.8 for details regarding administration of the study intervention.

All placebos were created by the Sponsor to match the active product.

6.2 Preparation/Handling/Storage/Accountability

6.2.1 Handling, Storage, and Accountability

The investigator or designee must confirm appropriate temperature conditions have been maintained during transit for all study intervention received, and any discrepancies are reported and resolved before use of the study intervention.

Only participants enrolled in the study may receive study intervention, and only authorized site staff may supply or administer study intervention. All study interventions must be stored in a secure, environmentally controlled, and monitored (manual or automated) area in accordance with the labeled storage conditions with access limited to the investigator and authorized site staff.

The investigator, institution, or the head of the medical institution (where applicable) is responsible for study intervention accountability, reconciliation, and record maintenance (ie, receipt, reconciliation, and final disposition records).

For all study sites, the local country Sponsor personnel or designee will provide appropriate documentation that must be completed for drug accountability and return, or local discard and destruction if appropriate. Where local discard and destruction is appropriate, the investigator is responsible for ensuring that a local discard/destruction procedure is documented.

The study site is responsible for recording the lot number, manufacturer, and expiry date for any locally purchased product (if applicable) as per local guidelines unless otherwise instructed by the Sponsor.

The investigator shall take responsibility for and shall take all steps to maintain appropriate records and ensure appropriate supply, storage, handling, distribution, and usage of study interventions in accordance with the protocol and any applicable laws and regulations.

6.3 Measures to Minimize Bias: Randomization and Blinding

6.3.1 Intervention Assignment

Participants will be assigned randomly according to a computer-generated allocation schedule in a 3:1 ratio within each Panel. The sample allocation schedules are provided in Table 2, Table 3 and Table 4.

Table 2 Panel A (healthy participants) and Panel B (participants with schizophrenia: monotherapy) Sample Allocation Schedule

Panel	n	Days 1-3	Days 4-6	Days 7-9	Days 10-12	Days 13-15	Days 16-18
A ^a	12	4 mg	8 mg	12 mg	16 mg	20 mg	24 mg
	4	PBO	PBO	PBO	PBO	PBO	PBO
B ^b	12	4 mg	8 mg	12 mg	16 mg	20 mg	24 mg
	4	PBO	PBO	PBO	PBO	PBO	PBO

a. Panel A allocation schedule will be stratified to Japanese and non-Japanese participants. Japanese participants will be assigned the lower allocation range (first 8 numbers) and non-Japanese will be assigned the upper allocation range (last 8 numbers). This will allow an equal number of active and placebo within the Japanese and non-Japanese participants.

b. Panel B allocation schedule will not be stratified

Table 3 Panel C (participants with schizophrenia; add-on therapy) Sample Allocation Schedule

Panel	n	Days 1-3	Days 4-6	Days 7-9	Days 10-12	Days 13-15	Days 16-18
C	9	4 mg	8 mg	12 mg	16 mg	20 mg	24 mg
C	3	PBO	PBO	PBO	PBO	PBO	PBO

Table 4 Panel D (participants with schizophrenia: monotherapy) Sample Allocation Schedule

Panel	n	Days 1-3	Days 4-6	Days 7-9	Days 10-12	Days 13-15
D	12	8 mg	16 mg	24 mg	36 mg	48 mg
D	8	PBO	PBO	PBO	PBO	PBO

6.3.2 Stratification

Intervention allocation/randomization will be stratified based on ethnicity for Panel A.

No stratification based on age, sex, or other characteristics will be used for Panel B, Panel C and Panel D.

6.3.3 Blinding

A double-blinding technique will be used. MK-8189 and placebo will be prepared and/or dispensed in a blinded fashion by an unblinded pharmacist or qualified study site personnel. The participant and the investigator who is involved in the study intervention administration or clinical evaluation of the participants are unaware of the group assignments.

6.4 Study Intervention Compliance

Administration of study medication will be witnessed by the investigator and/or study staff.

6.5 Concomitant Therapy

Concurrent use of any prescription or nonprescription medication, during the ongoing study (i.e., after randomization or intervention allocation) must first be discussed between the investigator and Sponsor prior to administration, unless appropriate medical care necessitates that therapy or vaccination should begin before the investigator and Sponsor can consult. The participant will be allowed to continue in the study if both the Sponsor and the investigator agree.

Paracetamol/acetaminophen and antacids (e.g. magnesium hydroxide) may be used for minor ailments without prior consultation with the Sponsor. Note: for participants in Panel C, the investigator should confirm the use of antacids should not interact with participant's AAP as per the AAP prescribing information.

For participants with schizophrenia (Panel B, Panel C and Panel D), medications to treat mild chronic conditions such as hypothyroidism, diabetes, high blood pressure, chronic respiratory conditions or other mild medical conditions are allowed during the study if the prescribed dose and regimen of medication is stable for at least three months prior to screening and there are no expected changes in co-medication during the study. Moderate to strong inhibitors or inducers of ^{CCI} [redacted] and/or ^{CCI} [redacted] are not allowed as ^{CCI} [redacted].

[redacted] In addition, MK-8189 is a mild inducer of ^{CCI} [redacted] in human hepatocytes at drug concentrations of $\geq 10 \mu\text{M}$ and therefore co-medication with substrates for ^{CCI} [redacted] should be avoided (^{CCI} [redacted]).

For Panel C only, subjects will continue the use of their permitted AAP medication (i.e., use of risperidone > 6 mg/day or use of clozapine is not permitted).

For healthy participants (Panel A), no concomitant medication/vaccinations are permitted, except for the necessary treatment of AEs (see also Section 6.5.1 on rescue medication).

6.5.1 Rescue Medications and Supportive Care

For the treatment of EPS, such as **acute dystonia**, all participants may be treated with an anticholinergic. If the symptoms are unresponsive to anticholinergic treatment, a benzodiazepine can be used.

In case the participant presents with signs of **akathisia** without signs of dystonia, the participant can be treated with a β -adrenergic blocker. If symptoms do not disappear with the β -adrenergic blocker, treatment with an anticholinergic may be used. An anticholinergic may be used as first-line treatment in the case that a β -adrenergic blocker is not a preferred treatment based on a participant's medical history and/or concomitant medication.

Anticholinergics benzodiazepines and β -adrenergic blockers are often used in the treatment of EPS and are considered standard practice. Oral anticholinergic treatment is also used as concomitant medication to prevent EPS symptom with antipsychotic medication.

Panel B and Panel D participants will be washed off from their antipsychotic treatment. The duration of washout period should be at least 5 days or cover at least 3 half-lives of the drug (whichever is longer) prior to Day -1 assessments (this includes any rescue medication given during the washout period). During the washout and treatment period, a benzodiazepine and zolpidem may be used to treat withdrawal symptoms. The drugs indicated above should not be inhibitors or inducers of CYP3A and CYP2C9 (see Section 6.5 for further details), thus no effect on the PK of MK-8189 would be expected during co-administration.

6.6 Dose Modification (Escalation/Titration/Other)

All dose titration decisions will be made jointly by the investigator and the Sponsor. Each dose titration decision for each individual participant will occur after 3 days of dosing per dose level.

Dose titration decisions for each participant will be based on available (as per the SoA) safety variables: VS, 12-lead safety ECG, laboratory safety tests, AEs, C-SSRS, BPRS, and EPS evaluations from the previous dose levels. Pharmacokinetic and pharmacodynamic data may be included in the dose titration decisions.

If, as judged by the Sponsor and investigator, the safety and tolerability data do not justify dose titration, the dose will not be increased as planned. Instead, participants may:

- Skip a single dose and dosing may continue at the same dose level or adjusted downwards
- Receive the same dose level to further explore safety and tolerability at that level
- Receive a lower dose of the study intervention

- Dosing may be stopped

If appropriate medical care necessitates dosing to be stopped or a lower dose given, the investigator may do so without consultation with the Sponsor.

Participant discontinuation criteria are outlined in Section 7.

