 - If a subject discontinues study treatment at a dose of 12 mg or higher, an attempt should be made to collect 24-hour Holter data through 48 hours following their last dose.
- g. For Panel C, triplicate 12-lead safety ECG measurements will be taken 1-2 minutes apart at all timepoints. On the following days, specific timepoints are noted:
- Day 1: within 2 hours prior to dosing
 - Day 9, Day 12, Day 13, Day 15, Day 16 and Day 18: 8, 10, 16 and 24 hours post-dose
- h. In the event the urine pregnancy test is positive or cannot be confirmed negative, a serum pregnancy test will be required.
- i. Screening UDS is mandatory; any additional UDS are conducted per site SOP. UDS prior to randomization will be done on the day of admission.
- j. Scheduled assessments are completed predose on dosing days and at any time on non-dosing days.
- k. Additional BARS, AIMS and SAS assessments will be conducted when observed or reported complaints of dystonia and/or akathisia occur.
- l. MK-8189 plasma PK sample collection (note: when time point coincides with Holter extraction, the PK sample will be collected as soon as possible after Holter extraction but must be collected after any vital sign assessments):
- Panel A and B and C: Day 1 and Day 4: pre-dose.
 - Panel A and B: Day 7, Day 10, Day 13 and Day 16: predose, 2, 6, 8, 10, 12, 16 and 24 hours post-dose
 - Panel C: Day 9, Day 12, Day 15; predose, 2, 6, 8, 10, 12, 16 and 24 hours post-dose.
 - Panel A and B and C: Day 18: 2, 6, 8, 10, 12, 16, 24, 36 and 48 hours post-dose
 - Optional sample when signs of dystonia and/or akathisia occur
 - If a subject discontinues study treatment at a dose of 12 mg or higher, an attempt should be made to collect PK samples through 48 hours following their last dose.
 - Leftover main study plasma will be stored for future biomedical research if the participant consents to future biomedical research.
- m. In Panels A and B, assessments will be done on Day -2. In Panel C, assessments will be done on Day -1.

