8.1.11 Participant Blinding/Unblinding

STUDY INTERVENTION IDENTIFICATION INFORMATION IS TO BE UNMASKED ONLY IF NECESSARY FOR THE WELFARE OF THE PARTICIPANT. EVERY EFFORT SHOULD BE MADE NOT TO UNBLIND.

For emergency situations where the investigator or medically qualified designee (consistent with local requirements) needs to identify the drug used by a participant and/or the dosage administered, he/she will contact the emergency unblinding call center by telephone and make a request for emergency unblinding. As requested by the investigator or medically qualified designee, the emergency unblinding call center will provide the information to him/her promptly and report unblinding to the Sponsor. Prior to contacting the emergency unblinding call center to request unblinding of a participant's treatment assignment, the investigator who is qualified physician should make reasonable attempts to enter the intensity of the AEs observed, the relation to study drug, the reason thereof, etc., in the medical chart. If it is not possible to record this assessment in the chart prior to the unblinding, the unblinding should not be delayed.

In the event that unblinding has occurred, the circumstances around the unblinding (eg, date, reason, and person performing the unblinding) must be documented promptly, and the Sponsor Clinical Director notified as soon as possible.

Once an emergency unblinding has taken place, the principal investigator, site personnel, and Sponsor personnel may be unblinded so that the appropriate follow-up medical care can be provided to the participant.

Participants whose treatment assignment has been unblinded by the investigator or medically qualified designee and/or nonstudy treating physician must be discontinued from study intervention, but should continue to be monitored in the study.

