8.6 Pharmacokinetics

The decision as to which plasma samples collected will be assayed for evaluation of PK/PD will be collaboratively determined by the Sponsor (e.g., samples at lower doses may not be assayed if samples at higher doses reveal undetectable drug concentrations). If indicated, these samples may also be assayed and/or pooled for assay in an exploratory manner for metabolites and/or additional PD markers.

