8.12 Study Design/Dosing/Procedures Modifications Permitted Within Protocol Parameters

This is a Phase 1 assessment of MK-8189 in humans, and the PK, PD, and safety profiles of the compound are still being elucidated. This protocol is written with some flexibility to accommodate the inherent dynamic nature of Phase 1 clinical studies. Modifications to the dose, dosing regimen, and/or clinical or laboratory procedures currently outlined may be required to achieve the scientific goals of the study objectives and/or to ensure appropriate safety monitoring of the study participants.

As such, some alterations from the currently outlined dose and/or dosing regimen may be permitted based on newly available data, but the maximum daily dose may not exceed those currently outlined in the protocol.

- Repeat of or decrease in the dose and/or titration steps of the study intervention administered in any given day/panel.
- Entire panel may be omitted.
- Adjustment of the dosing interval (e.g., divided doses [BID to QD, QD to BID, TID, or vice versa]).
- Instructions to take study intervention with or without food or drink may also be modified based on newly available data.
- Modification of the PK/PD sample processing and shipping details based on newly available data.
- A single dose may be skipped, and dosing may continue at the same dose level or adjusted downwards.

The PK/PD sampling scheme currently outlined in the protocol may be modified during the study based on newly available PK or PD data (e.g., to obtain data closer to the time of peak plasma concentrations). If indicated, these collected samples may also be assayed in an exploratory manner for metabolites and/or additional PD markers.

Up to additional 50 mL of blood may be drawn for safety, PK, and/or PD analyses. The total blood volume withdrawn from any single participant will not exceed the maximum allowable volume during his/her participation in the entire study (Section 10.10).

The timing of procedures for assessment of safety procedures (e.g., VS, ECG, safety laboratory tests, etc.) may be modified during the study based on newly available data.

Additional laboratory safety tests may be added to blood samples previously drawn to obtain additional safety information. These changes will not increase the number of study procedures for a given participant during his/her participation in the entire study.

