10.2 Appendix 2: Clinical Laboratory Tests

- The tests detailed in [Table 6](#) will be performed by the local laboratory.
- Protocol-specific requirements for inclusion or exclusion of participants are detailed in Section 5 of the protocol.
- Additional tests may be performed at any time during the study as determined necessary by the investigator or required by local regulations.
- Pregnancy testing:
 - Pregnancy testing requirements for study inclusion are described in Section 5.1.
 - Pregnancy testing (urine or serum as required by local regulations) should be conducted at the end of relevant systemic exposure and correspond with the time frame for female participant contraception in Section 5.1.
 - Additional serum or urine pregnancy tests may be performed, as determined necessary by the investigator or required by local regulation, to establish the absence of pregnancy at any time during the subject's participation in the study.

Table 6 Protocol-required Safety Laboratory Assessments

Laboratory Assessments	Parameters			
Hematology	Platelet Count	WBC count with Differential: Neutrophils Lymphocytes Monocytes Eosinophils Basophils		
	RBC Count			
	Hemoglobin			
	Hematocrit			
Chemistry	Blood Urea Nitrogen (BUN)	Potassium	Aspartate Aminotransferase (AST)/ Serum Glutamic-Oxaloacetic Transaminase (SGOT)	Total bilirubin (and direct bilirubin, if total bilirubin is elevated above the upper limit of normal)
	Albumin	Bicarbonate	Chloride	Phosphorous
	Creatinine	Sodium	Alanine Aminotransferase (ALT)/ Serum Glutamic-Pyruvic Transaminase (SGPT)	Total Protein
	Glucose (fasting)	Calcium	Alkaline phosphatase	
Routine Urinalysis	Specific gravity pH, glucose, protein, blood, ketones, [bilirubin, urobilinogen, nitrite, leukocyte esterase] by dipstick Microscopic examination (if blood or protein is abnormal)			

Laboratory Assessments	Parameters
Other Screening Tests	Follicle-stimulating hormone (as needed in women of nonchildbearing potential only) Urine alcohol, cotinine (Panel A only) and drug screen (to include at minimum: amphetamines, barbiturates, cocaine, opiates, cannabinoids and benzodiazepines; If the clinical site's drug screen evaluation routinely detects additional agents, the relevance of positive findings for exclusion will be discussed with the Sponsor.) Serum or urine β human chorionic gonadotropin (β hCG) pregnancy test (as needed for WOCBP) Serology (HIV antibody, hepatitis B surface antigen [HBsAg], and hepatitis C virus antibody)

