
• WBC Differential: absolute or % acceptable per institutional standard.• Creatinine: GFR (measured or calculated) or creatinine clearance can be used in place of creatinine. NOTES: The investigator (or medically qualified designee) must document their review of each laboratory safety report. Laboratory/analyte results that could unblind the study will not be reported to investigative sites or other blinded personnel until the study has been unblinded	

10.3 Appendix 3: Adverse Events: Definitions and Procedures for Recording, Evaluating, Follow-up, and Reporting

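### Does allowing PK data into individual titration decisions leave the blind unprotected?

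*Combined protocol and SAP*

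**What the plan says.** Section 6.6 lists the safety data that inform each participant's titration step and then allows that "Pharmacokinetic and pharmacodynamic data may be included in the dose titration decisions". It names neither the reader of the PK data nor its form (individual, pooled or coded).

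The text on blinding and on PK handling is spread over several places:

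- Section 6.3.3: the participant and the investigator involved in dosing or clinical evaluation "are unaware of the group assignments". The only unblinded role it describes is the pharmacist or qualified site person who prepares or dispenses the drug.
- Section 8.1.11: unmasking is reserved for the participant's welfare. After an emergency unblinding, "the principal investigator, site personnel, and Sponsor personnel may be unblinded" for follow-up care.
- Section 7.1: a participant whose assignment has been unblinded by the investigator, a subsidiary of the Sponsor or the call center must stop study intervention.
- Appendix 2, notes to Table 6: "Laboratory/analyte results that could unblind the study will not be reported to investigative sites or other blinded personnel until the study has been unblinded". The tests in that table "will be performed by the local laboratory", and MK-8189 concentration is not among them.
- Section 8.6: "The decision as to which plasma samples collected will be assayed for evaluation of PK/PD will be collaboratively determined by the Sponsor".
- Section 8.12: the sampling scheme "may be modified during the study based on newly available PK or PD data".
- Section 1.3, PK footnotes: "Optional sample when signs of dystonia and/or akathisia occur".

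The synopsis describes the study as double-blind and, in the next row, gives an entry for masking that says there is none.

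**The concern.** The investigator is blinded and is also a party to every titration decision. If individual concentrations are an allowed input, the natural form of that input tells the investigator which arm the participant is in. The one note that withholds unblinding results sits under a table of local safety tests and does not name MK-8189 levels. The blinding status of the Sponsor staff who share the decision is nowhere stated directly.

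Section 4.2.2 gives protection of adverse-event reporting and assessment from bias as a reason for having placebo. Section 8.3.8 has the investigator or a designee complete the BARS, AIMS and SAS. If arm-identifying levels reached these raters, the observer-rated safety data, which are primary, would lose that protection. The optional sample at signs of dystonia or akathisia adds to the worry, because it links a concentration to the very event being rated.

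**Working it through.** **1. How much a concentration reveals.** From Tables 2 to 4, active is 12 + 12 + 9 + 12 = 45 and placebo is 4 + 4 + 3 + 8 = 19. The sum is 64, which matches the synopsis. Before any PK result, the probability of active is 12/16 = 9/12 = 0.75 in Panels A to C and 12/20 = 0.60 in Panel D. Assuming that placebo samples are assayed and contain no MK-8189, one measurable post-dose level settles the arm. The ingredient for unblinding is real.

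**2. Whether results could arrive in time.** Panels A to C have 5 titration steps (Days 4, 7, 10, 13, 16) and Panel D has 4 (Days 4, 7, 10, 13). Planned decisions are 44 × 5 + 20 × 4 = 220 + 80 = 300. In Panels A and B the Day 7 profile ends on Day 8, two days before the Day 10 step, and later profiles follow the same pattern. In Panel D the Day 1 profile ends on Day 2, two days before the Day 4 step. In Panel C the profile ends on the day of the step.

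**3. Whether the exposure can be counted.** It cannot, because assay turnaround T is not in the documents. The count also depends on what is taken to be informative:

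| Information counted | Assumed T | Decisions reachable |
|---|---|---|
| Completed 24-hour profile | same day | 32×3 + 12×3 + 20×4 = 212 |
| Completed 24-hour profile | 1–2 days | 32×3 + 12×2 + 20×4 = 200 |
| Completed 24-hour profile | 12 days or more | 0 |
| Any single sample (Day 4 predose in A–C, Day 1 post-dose in D), if measurable | 1–3 days | 44×4 + 20×4 = 256 |
| Any single sample, if measurable | 12 days | 44×1 + 20×1 = 64 |

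These figures run from 0 to 256 of 300 according to assumptions the plan does not supply. They describe opportunity, not unblinding or bias, so no size should be drawn from them.

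**4. What the blinding rules require.** There are two readings of the Appendix 2 note.

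- *Broad reading.* The note speaks of analytes as well as laboratory results. Table 6 tests are run locally, and Section 8.3.6 requires the investigator to review the reports, so withholding results from sites fits those tests poorly. It fits an assay under Sponsor control (Section 8.6) well. On this reading, individual levels may not reach the investigator, and the permission in Section 6.6 covers only PK that does not identify the arm.
- *Narrow reading.* The note does not reach MK-8189 levels. Sections 6.3.3, 8.1.11 and 7.1 still apply. Routine release of arm-identifying levels to the investigator would contradict the first, fall outside the welfare condition of the second, and raise the discontinuation rule of the third.

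Both readings lead to the same conduct on the investigator's side.

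**5. The Sponsor's side.** Section 8.1.11 treats unblinding of Sponsor staff as something that may follow an emergency. Section 7.1 counts unblinding by a subsidiary. Sections 9.1 and 9.6 require the concentration-QTc modeling plan to be finished before the blind is broken, and Section 9.5 has important deviations identified before then as far as possible. Section 9.7 plans no interim analysis. None of these names the titration decision-makers, but all point to a Sponsor-side blind.

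**6. What the other passages add.** Section 8.12 permits a change of sampling, and its closing text says that some or none of the listed alterations may be used. The optional dystonia or akathisia sample is a collection item, and no passage returns its result to the rater. Under Section 8.7 the PD data are QTc and other ECG parameters, which do not reveal the arm as a drug level does.

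**The case for a change.** The best argument for a change is that a blind should not have to be pieced together from four places. The plan names an unblinded role for open-label supplies (Sections 6.3.3 and 6.8) but none for concentrations. On the broad reading of the Appendix 2 note, Section 6.6 seems to offer a blinded co-decider data that the note forbids. On the narrow reading, nothing mentions drug levels at all. Since unblinding leads to discontinuation, whether seeing a level counts as unblinding should be clear, and a few words would make it so.

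Part of this stands. Section 6.6 is silent on access and form, and the status of the Sponsor decision-makers is only implied. Naming MK-8189 concentrations would be tidier.

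It does not show that results would be unsound. The PK input is optional, and the stated ground for not escalating is safety and tolerability. Data-management procedures are kept in a separate document (Section 10.1.7), so an access rule may already exist. Should a level leak despite the rules, the effect would be confined to observer-rated adverse events and scales that are summarized descriptively. Holter tracings are read by a blinded core laboratory (Section 8.3.4).

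**Conclusion.** No change to the plan is needed. The silence in Section 6.6 is a missing detail that a Sponsor bound by Sections 6.3.3, 7.1 and 8.1.11 and the Appendix 2 note would fill in the same sensible way: arm-identifying concentrations stay away from the investigator and raters outside an emergency, and any PK used in titration takes a form that does not reveal the arm. Writing that down would record an access policy without altering sampling, analysis or results. The synopsis masking entry is a clerical error, contradicted by the row above it and by Section 6.3.3.

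The size is nil for every stated figure: the total of 64 reproduces, there are no hypotheses or power calculations (Sections 9.8 and 9.9), and no error rate is involved. The conclusion assumes that the Sponsor follows its own blinding rules and that the implied Sponsor-side blind extends to the staff who share titration decisions. The second assumption is the weaker one, because the documents do not state it.
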